4 HYPOTHESES AND DECISION RULES

4.1 STATISTICAL HYPOTHESES

This study have several aims however just the aim 2 has a tested hypothesis.

a. Null Hypothesis (H_0) :

H_0 : “The results of the detection of ALK gene re-arrangements obtained using NGS are not equal to those obtained from using Ventana®”.

b. Alternative Hypothesis (H_1) :

H_1 : “The results of the detection of ALK gene re-arrangements obtained using NGS are equal to those obtained from using Ventana®”.

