4.2 STATISTICAL DECISION RULES

In case of multiple testing P values thresholds will be computed with Benjamini- Hoshberg criterion and $FDR \leq 0.05$. For other cases P value ≤ 0.05

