5 ANALYSIS SETS/ POPULATIONS

The study population includes all patients who satisfy all inclusion and exclusion criteria. To test the hypothesis the results in NGS for ALK will be compared with those obtained in patients that present a positive results for Ventana®-ALK. Those NSCLC patients that are negative for Ventana®-ALK will be used to establish the levels of false positive. In general the level of concordance between both methods will be calculated.

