Each of the following methods could be affected differently by the proportion of positive and negative cases; therefore both methods will be used.

Simple Agreement: Simple agreement will be calculated as the concordance proportion for the positive cases (PPA), and the concordance proportion for the negative cases (NPA).

Specific Agreement:

To establish the specific agreement we will use two methods **McNemar’s Chi-Square** and **Cohen’s Kappa**. The objective is to establish the statistical significance (P-value) of the correlation between the results obtained for ALK using NGS y Ventana®. However, previous investigation establish that these methods tend to reject the hypothesis H0.

- **McNemar’s Chi-Square:** This method is easier to calculate and more precise when the discordance is small compared with the concordance agreement.

For the following variables:

	Test 2 Positive	Test 2 Negative	Totals
Test 1 Positive	a	b	n ₁ =a+b
Test 1 Negative	c	d	n ₂ =c+d
Totals	m ₁ =a+c	m ₂ =b+d	N=n ₁ +n ₂

Where, the null hypothesis is H₀: p_b=p_c and the alternative hypothesis is H₁: p_b≠p_c.

The McNemar’s test statistic with Yates' continuity correction is:

$$X^2 = \frac{(|b-c|-1)^2}{b+c} \quad , \text{ with degree of freedom } = 1$$

Under the null hypothesis, with a sufficiently large number of discordant (cells b and c), X^2 has a chi-squared distribution with 1 degree of freedom. If the X^2 result is significant, this provides sufficient evidence to reject the null hypothesis, in favour of the alternative hypothesis that $p_b \neq p_c$, which would mean that the marginal proportions are significantly different from each other. If either b or c is small ($b + c < 25$) then X^2 is not well-approximated by the chi-squared distribution and a modification at this method will be required.

Cohen’s Kappa: Kappa measures the percentage of data values in the main diagonal of the table and then adjusts these values for the amount of agreement that could be expected due to chance alone.

For the following variables:

The cell

	Test 2 Positive	Test 2 Negative	Totals
Test 1 Positive	a	b	$n_1=a+b$
Test 1 Negative	c	d	$n_2=c+d$
Totals	$m_1=a+c$	$m_2=b+d$	$N=n_1+n_2$

table below contains

probabilities (P) of each type of results in 2 by 2 table.

To

	Test 2 Positive	Test 2 Negative	Totals
Test 1 Positive	P_a	P_b	
Test 1 Negative	P_c	P_d	
	$P_{(a+c)}$	$P_{(b+d)}$	1

calculate Kappa, first is

necessary to calculate the observed level of agreement $P_0 = P_a + P_d$

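### The null hypothesis for the only tested aim runs opposite to McNemar's null, no deciding test is named, and neither planned P-value can establish ALK agreement

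*SAP*

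**What the plan says.** SAP 4.1 limits formal testing to aim 2 and states the null as "The results of the detection of ALK gene re-arrangements obtained using NGS are not equal to those obtained from using Ventana"; the alternative is that the results are equal. SAP 4.2 supplies the decision rule: "In case of multiple testing P values thresholds will be computed with Benjamini- Hoshberg criterion" at an FDR of 0.05, and otherwise "For other cases P value ≤ 0.05".

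SAP 8.1b (Concordance methods) supplies the tests: "To establish the specific agreement we will use two methods", McNemar's chi-square and Cohen's kappa. McNemar's null is given as p_b = p_c, and a significant result is read as one "which would mean that the marginal proportions are significantly different from each other". When b + c < 25, "a modification at this method will be required", but the modification is not named. No null value, minimum or standard error is given for kappa; it is compared with what independence of the two methods would give. The SAP remarks that these methods tend to reject H0, without saying which H0.

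SAP 5 adds: "To test the hypothesis the results in NGS for ALK will be compared with those obtained in patients that present a positive results for" Ventana ALK, while the Ventana-negative patients "will be used to establish the levels of false positive".

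PPA, NPA, sensitivity and specificity are also planned, with no pass mark. The sample-size part of SAP 8.1 has a sensitivity cut-off above 0.8 and names a minimal specificity without a value. Neither enters the decision rule.

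**The concern.** Under 4.1 and 4.2 a small P-value supports equality. Under 8.1b a small McNemar P-value supports a difference. The two nulls are not exact complements (4.1 concerns the results, McNemar only the marginal rates), but they point in opposite directions. Kappa's usual null, chance agreement, points the same way as 4.1. A reader holding both P-values therefore has no stated way to reach a conclusion on aim 2. Benjamini-Hochberg adjusts thresholds; it does not rank tests or settle conflicts. SAP 5 adds to the uncertainty, because it frames the hypothesis in Ventana-positive patients while both statistics need the full 2×2 table.

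Turning 4.1 round would not cure this. McNemar compares only the two discordant cells with each other, so it is silent on how much disagreement there is. A kappa test against zero shows only that agreement beats chance. At stake is the single formal conclusion on the protocol's primary objective: the same data could be reported as equal or different according to the section followed, and that choice could be made after the results are seen.

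**Working it through.** **Inputs.** The visible SAP gives no N, power or critical value for either test, so there is no stated figure to reproduce. The re-assessed sample size is in appendices listed by title only. I assumed N = 3000 (protocol abstract) and 120 ALK-positive (protocol 7.4). The abstract's tentative 40 per 1000 scales to the same count: 0.04 × 3000 = 120. The cell counts are illustrations.

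**Notation.** a = both positive, b = NGS+/Ventana−, c = NGS−/Ventana+, d = both negative. PPA = a/(a+c); NPA = d/(b+d).

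**McNemar, SAP formula** X² = (|b−c|−1)²/(b+c), 1 df:
- b = c = 60: 1/120 = 0.0083
- b = 8, c = 0: 49/8 = 6.125
- b = c = 2: 1/4 = 0.25

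**Kappa, standard formula** (Po−Pe)/(1−Pe):
- b = c = 60: Po = 2880/3000 = 0.96; Pe = 0.04² + 0.96² = 0.9232; kappa = 0.0368/0.0768 = 0.479.
- b = 8, c = 0: Po = 2992/3000 = 0.9973; Pe = (128/3000)(0.04) + (2872/3000)(0.96) = 0.9208; kappa = 0.966. The SAP's printed Pe gives 0.965.

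| Table (a, b, c, d) | PPA | NPA | Kappa | McNemar P (exact) | P against chance |
|---|---|---|---|---|---|
| 1: 60, 60, 60, 2820 | 50% | 97.9% | 0.48 (95% CI 0.40–0.56) | 0.93 (1.0) | about 1e-57 |
| 2: 120, 8, 0, 2872 | 100% | 99.7% (Wilson 99.45–99.86%) | 0.97 (0.94–0.99) | 0.013 (0.008) | about 6e-206 |
| 3: 118, 2, 2, 2878 | 98.3% | 99.9% | 0.98 | 0.62 (1.0) | < 0.0001 |

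For tables 1 and 2 the chance test is a one-sided Fisher exact test; for table 3 it is kappa's large-sample test. Both take kappa = 0 as the null.

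**Reading these under the plan.**
- Table 1: McNemar finds nothing although half the positives are missed, while kappa rejects chance. The two P-values fall on opposite sides of 0.05.
- Table 2: McNemar is significant. Under 8.1b the assays differ; put into 4.1's rule, the same P-value declares them equal.
- Table 3: close to perfect and balanced, yet McNemar would not reject 4.1's null.
- Six one-sided discordant samples suffice for significance at any N: exact P = 2 × 0.5⁶ = 0.031. Five give 0.0625.

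**Multiplicity.** With the two P-values as one Benjamini-Hochberg family (thresholds 0.025 and 0.05), table 1 rejects only kappa and table 2 rejects both. Nothing is resolved.

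**Smaller study** (1000 patients, 40 positive): b = c = 20 gives McNemar P = 0.87 with kappa 0.48; b = 8, c = 0 gives exact P = 0.008 with PPA 100%, NPA 99.2% and kappa 0.90.

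**The case against.** **The estimates carry the science.** PPA, NPA, sensitivity, specificity and kappa are all planned, protocol 7.4 cites Wilson intervals, and no patient is treated under the protocol. On this view only the label on a P-value is damaged. It is true that poor agreement would be visible. But the SAP defines a formal test for its concordance aim, and that test has no coherent reading.

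**The direction of 4.1 is sound.** A null of disagreement is the normal way to demonstrate agreement; what is missing is a margin in 4.1 and a suitable test in 8.1b. This stands, and the proposed replacement keeps that direction.

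**Table 1 needs balanced errors.** With c = 60, the SAP's formula gives P > 0.05 only for b from 40 to 84 (NPA about 98.6% to 97.1%). At b = 29, P = 0.0015; at b = 0, X² = 59²/60 = 58.0 and P = 2.6e-14. This limits how often McNemar would miss poor agreement. It does not help the plan: under 4.1's rule, b = 0 with half the positives missed would be a highly significant finding of equality.

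**Kappa's null is assumed.** A test against a preset non-zero kappa could support agreement. None is stated, and the SAP's only reference value is independence.

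**The SAP intends several measures together.** It says both methods will be used because prevalence affects them differently. That explains the choice but gives no rule for when they conflict.

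**Conclusion.** The concern holds and must be fixed. The opposite direction is explicit in SAP 4.1 and 8.1b and rests on no assumption. The absence of a deciding test holds for the visible text; Appendices 3–8 could contain a rule, but their content is not shown. That McNemar's P-value cannot establish agreement follows from its stated null. For kappa it rests on the usual null of zero.

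The size is illustrated on assumed tables: McNemar P = 0.93 at PPA 50%, and P = 0.013 at PPA 100% with NPA 99.7%, while kappa rejects chance in both. The harm is confined to the formal conclusion on aim 2; the descriptive estimates remain usable.

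**What to change.** 1. Remove the equal/not-equal P-value rule for aim 2. Base the conclusion on PPA and NPA together, each with a two-sided Wilson interval (the method protocol 7.4 cites) at a stated confidence level.

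2. If a formal test is kept, use H0: PPA ≤ 0.80 against H1: PPA > 0.80, adopting the SAP's own sensitivity cut-off, and call it a sensitivity claim only. Requiring the Wilson lower limit to exceed 0.80 gives:

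| Positives | Level | Needed | Lower limit | Power at PPA 0.90 / 0.95 |
|---|---|---|---|---|
| 120 | 95% | 105 | 0.804 | 0.86 / 0.9997 |
| 120 | 99% | 108 | 0.807 | 0.58 / 0.99 |
| 40 | 95% | 37 | 0.801 | 0.42 / 0.86 |
| 40 | 99% | 39 | 0.818 | 0.08 / 0.40 |

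The 99% level is the one named in the sample-size section. At 95% the one-sided type I error is 0.022 with 120 positives and 0.028 with 40, slightly above the nominal 0.025.

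3. Do not claim concordance from PPA alone. An assay calling all 3000 samples positive passes (PPA 100%, kappa 0), as does 105/120 with NPA 90% (288 false positives, PPV 105/393 = 27%, kappa 0.37). The sponsor must set an NPA minimum; the documents give none. As a guide, with 114/120 detected and 2880 Ventana-negative:

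| NPA | False positives | PPV | Kappa |
|---|---|---|---|
| 95% | 144 | 44% | 0.58 |
| 99% | 29 | 80% | 0.86 |
| 99.5% | 14 | 89% | 0.92 |

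If both limits must be met, the pair needs no multiplicity adjustment. Without an NPA minimum, report NPA as an estimate and make no pass/fail claim of concordance.

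4. Keep McNemar (H0: p_b = p_c, exact version when b + c < 25) as a secondary check for directional imbalance. Report kappa with a confidence interval, and do not use its P-value as evidence of agreement.

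**Cost.** A SAP revision, and possibly a protocol amendment under protocol 7.6; no new patients or data. Power is low if positives are few. SAP v2.0 (10 July 2019) postdates the planned end of data collection (30 June 2019), so any limit added now should be dated and labelled as set at that point, not presented as pre-specified from the start.

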4.2 STATISTICAL DECISION RULES

In case of multiple testing P values thresholds will be computed with Benjamini- Hoshberg criterion and $FDR \leq 0.05$. For other cases P value ≤ 0.05

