6 ENDPOINTS AND COVARIATES

a. Primary Endpoint.

- **Primary endpoint 1:** Obtaining results / diagnosis of NGS and Ventana for the ALK biomarker.
- **Primary endpoint 1:** Analysis of NGS y Ventana for ALK.

b. Secondary Endpoints

Secondary endpoint 1: PE1 in prospective and retrospective patients.

Secondary endpoint 2: PE1 in smokers and non-smokers.

Secondary endpoint 3: PE1 depending on the location, stage and histological classification of the biopsy

Secondary endpoint 4: PE1 in patients of different gender and age.

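### SAP 4.2 leaves the Benjamini-Hochberg family undefined; if it covers subgroup McNemar tests, it makes real NGS–Ventana differences harder to flag, and a non-significant McNemar result is not evidence of agreement

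*SAP*

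**What the plan says.** SAP 4.2 is a general rule in two parts. Under multiplicity, "In case of multiple testing P values thresholds will be computed with Benjamini- Hoshberg criterion" with a false discovery rate of at most 0.05; then "For other cases P value ≤ 0.05". It lists no tests, endpoints or family size.

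The rest has to be pieced together from other sections:

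- SAP 4.1: "This study have several aims however just the aim 2 has a tested hypothesis". Aim 2 is ALK concordance. Its null hypothesis is "The results of the detection of ALK gene re-arrangements obtained using NGS are not equal to those obtained from using Ventana", so rejecting it would mean that the assays are equal.
- SAP 6 repeats primary endpoint 1 in subgroups, beginning with "Secondary endpoint 1: PE1 in prospective and retrospective patients" and continuing with smoking, tumour location, stage, histology, gender and age. It names no test or decision rule for these.
- SAP 8.1: "To establish the specific agreement we will use two methods", namely McNemar and Cohen's kappa. For McNemar the null is equal discordant probabilities, and the SAP explains a significant result as one "which would mean that the marginal proportions are significantly different from each other". This is the reverse of the hypotheses in SAP 4.1.
- SAP 8.1 also plans PPA, NPA, sensitivity, specificity, PPV and accuracy, but does not say that they will be given by subgroup and sets no acceptance limit for subgroup agreement.

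**The concern.** A false-discovery correction guards against declaring effects that are not there. For McNemar the declared effect is a difference between NGS and Ventana. In an assay validation the costly error is the opposite one: accepting NGS where it fails. Lowering the P threshold makes that error more likely, and increasingly so as subgroups are added.

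Secondary endpoint 1 shows what is at stake. Archived tissue is where one might worry about RNA quality, and the prospective/retrospective comparison is where a loss of NGS sensitivity would appear. If the P value is the main summary, a real loss could be reported as no significant difference. The SAP does not say how such a result is to be read.

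**Working it through.** **No derived figure to reproduce.** The 0.05 thresholds are chosen, not calculated. As a consistency check on prevalence, the protocol's Abstract expects 40 ALK-positives in 1000 and 120 from at least 3000 screened: 40/1000 = 120/3000 = 4%.

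**Size of the family.** SAP 5.4 gives 2 levels each for prospective/retrospective, smoking and gender, and 4 for age: 2 + 2 + 2 + 4 = 10. The 8 stages in SAP 6.4 make 18. Location and histology levels are not given; assuming 2 each makes 22. If each secondary endpoint is its own family, endpoint 1 has 2.

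**Direction.** Let b be Ventana-positive/NGS-negative cases (misses) and c the reverse (NGS false positives against Ventana). The SAP's statistic is X² = (|b − c| − 1)²/(b + c), and the smallest Benjamini-Hochberg threshold is 0.05/m. With c = 0, X² = (b − 1)²/b:

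| m | Smallest threshold | Misses needed, Yates | Misses needed, exact |
|---|---|---|---|
| 1 | 0.05 | 6 (25/6 = 4.17) | 6 |
| 10 | 0.005 | 10 (81/10 = 8.10) | 9 |
| 18 | 0.0028 | 11 (100/11 = 9.09) | 10 |

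More subgroups therefore mean that more misses are needed before a difference is flagged.

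**A typical case.** Assume N = 3000, 4% prevalence, half retrospective, and in that half sensitivity 0.80 and 0.1% false positives. Then:

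- Retrospective ALK-positives: 1500 × 0.04 = 60.
- Expected misses: 60 × 0.20 = 12.
- Expected false positives: 1440 × 0.001 = 1.4.

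Take b = 12 and c = 1. X² = (11 − 1)²/13 = 7.69, P = 0.0055; the exact two-sided P is 2 × (1 + 13)/2¹³ = 0.0034. Both pass 0.05 and 0.025. At 0.005 Yates fails and exact passes. At 0.05/22 = 0.0023 both fail. (Benjamini-Hochberg is a step-up rule, so a subgroup's threshold is looser when other subgroups are also significant.)

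**Simulation of the same case**, with sensitivity 0.98 in prospective tissue. Chance of flagging the retrospective group:

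| Test | Unadjusted | 2 tests | 10 tests | 22 tests |
|---|---|---|---|---|
| Yates | 80% | 67% | 43% | 33% |
| Exact | 81% | 72% | 51% | 42% |

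Repeat runs with different assumed stage and age mixes agreed within a few points. Both tests are shown because SAP 8.1 says the chi-square approximation is poor when b + c < 25 and leaves the modification open. Here b + c is below 25 in 97–100% of replicates.

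**Other inputs** (10 Yates tests, specificity 0.9995, 120 ALK-positives). If NGS fails in one half-sample only, detection there falls from 91% to 57% at sensitivity 0.80 and from 38% to 5% at 0.90. If it fails everywhere, detection falls from about 92% to 85%, or from 37% to 12%.

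**What McNemar misses without any correction.** Take 120 ALK-positives with b = c = 24. Sensitivity is 96/120 = 0.80 and PPV is 96/(96 + 24) = 0.80, yet X² = 1/48 = 0.02 and P is about 0.89. With sensitivity 0.80 everywhere and specificity 0.9917 (about 24 misses against 24 false positives), a subgroup is flagged in at most 3% of trials unadjusted and 0.4% corrected.

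**The case against.** A reader might infer that the SAP applies the correction to subgroup McNemar tests, reads non-significance as equality, and so hides NGS failures. The documents do not support that chain.

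- **Family.** SAP 4.2 names no family. With one tested aim, the subgroups could be purely descriptive, and the correction would never operate on them. If each secondary endpoint is its own family, endpoint 1 loses only about 9 to 13 points. This stands: coverage of the subgroup McNemar tests is an inference.
- **Reading of non-significance.** SAP 8.1 says only what a significant McNemar result means. This stands too. However, equality is the alternative in SAP 4.1, P values are the only decision rule in SAP 4.2, and no other acceptance rule is given, so the gap invites that reading.
- **Visibility.** PPA, NPA and sensitivity are planned and would show a retrospective sensitivity near 0.80 whatever the P value, if they are reported by subgroup. So a loss would be non-significant rather than hidden.
- **Kappa.** A small kappa P value supports agreement beyond chance, so correction makes that claim harder. The correction therefore does not ease an agreement claim across both tests, although agreement beyond chance is a weak requirement.
- **Dropping the correction.** Unadjusted tests would raise false flags: 1 − 0.95¹⁰ = 40% or 1 − 0.95¹⁸ = 60% family-wise if independent. Balanced discordance would still go unseen. This stands, and it is why exempting McNemar alone is not enough.

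**Conclusion.** The concern holds conditionally. The SAP does not define the Benjamini-Hochberg family or say how a non-significant McNemar result is read. If the rule covers McNemar tests across the subgroups, which is the natural reading, it works in the unhelpful direction: fewer real differences are flagged, while the conclusion sought is equality.

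In the main illustration the loss of detection runs from about 10 points (2 tests, exact) to nearly 50 (22 tests, Yates). Sensitivities, false-positive rates, subgroup shares and the larger family are assumptions, so these figures show direction and range and do not forecast this study's results.

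The correction is not the root of the problem. McNemar tests whether the two assays have equal positive rates, not whether they agree case by case, and its null is reversed relative to SAP 4.1. The point concerns the secondary endpoints and how they are reported; it does not show that the study would wrongly validate NGS.

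**What to change.** In SAP 4.2 and 8.1:

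1. State that agreement is not concluded from a non-significant McNemar result, adjusted or not.
2. Treat McNemar as a descriptive check for directional bias, outside the Benjamini-Hochberg family, and list the tests that the family does contain.

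For secondary endpoints 1–4:

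3. Report PPA and NPA in each subgroup with 95% Wilson intervals, the method Protocol 7.4 already cites for sensitivity and specificity.
4. Claim agreement only where the lower PPA limit exceeds a pre-stated minimum; otherwise call the subgroup inconclusive. The 0.8 sensitivity cut-off in SAP 8.1 is a natural candidate, but it is used there for sample-size planning and would have to be adopted expressly for this purpose.

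With 60 retrospective ALK-positives, 48/60 gives 0.68–0.88 (agreement not claimed) and 59/60 gives 0.91–1.00 (claimed).

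The cost is a few sentences and no new data. Small subgroups will be inconclusive: when all n cases agree, the Wilson lower limit is n/(n + 1.96²), so 15/15 gives 15/18.84 = 0.796, and a subgroup with about 15 or fewer ALK-positives cannot reach 0.8. Unadjusted intervals will also give some chance flags of disagreement, which the report should acknowledge.

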5 ANALYSIS SETS/ POPULATIONS

The study population includes all patients who satisfy all inclusion and exclusion criteria. To test the hypothesis the results in NGS for ALK will be compared with those obtained in patients that present a positive results for Ventana®-ALK. Those NSCLC patients that are negative for Ventana®-ALK will be used to establish the levels of false positive. In general the level of concordance between both methods will be calculated.

5.1 FULL ANALYSIS SET

The final study population will include any NSCLC patients who satisfy all inclusion and exclusion criteria.

5.2 SAFETY ANALYSIS SET

Not Applicable

5.3 OTHER ANALYSIS SET

Not Applicable

5.4 SUBGROUPS

- The patients will be considered **RETROSPECTIVE** in those whose sample was taken before the date of signature of the IC. Meanwhile, patients whose samples were taken after the IC will be called **PROSPECTIVE**
- Based on their smoking habits, patients will be grouped into smoker or no-smokers.
- Subgroups will be considered depending on the characteristics of the samples concerning the location of the tumors, their stage and the histological classification of the biopsy.
- Different subgroups will be considered according to their gender (female/male) and different age ranges (18-30 / 31-40 / 41-60 / 60 and more).

